8.2.2. Planned Pharmacodynamic Statistical Analyses

Planned Statistical Analyses
Endpoint(s)

 • PIP3 Peak Area proportion (calculated as a proportion of the sum of PIP2 Peak Area and PIP3 Peak Area i.e. $\text{PIP3 Peak Area} / (\text{PIP2 Peak Area} + \text{PIP3 Peak Area})$)
Model Specification

 • Repeated measures analysis based on the two replicates for each subject on each study day. • Replicates are to be modeled using VC (variance components) structure • Response variable: $\text{Loge}(\text{PIP3 Peak Area proportion})$. The following will be included as fixed effects: Part A: period, treatment*daytime Part B: treatment*daytime*base Where daytime can take the values: Part A: 'Day 1 3h', 'Day 1 24h' Part B: 'Baseline', 'Day 1 3h', 'Day 1 24h', 'Day 12 3h', 'Day 12 24h' • Daytime and subject will be fitted as random effects
Model Checking

 • Refer to Appendix 8: Model Checking and Diagnostics for Statistical Analyses.

Planned Statistical Analyses
Model Results Presentation

• Adjusted geometric means for each treatment group will be presented along with 90% confidence intervals (CIs).• Part A: Point estimates of the treatment differences versus placebo and their associated 90% CIs will be calculated for both timepoints (using the pooled estimate of variance) and back transformed to provide estimates and 90% CIs for the treatment ratios.• Part B: Point estimates of the daytime differences versus placebo and their associated 90% CIs will be calculated (using the pooled estimate of variance) and back transformed to provide estimates and 90% CIs for the treatment ratios at each timepoint.• Bayesian posterior probabilities of seeing differences from placebo less than 0 (ratio less than 1) will be displayed.• Adjusted geometric means (for each treatment group and timepoint) and treatment ratios, along with 90% CIs will be plotted.

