10.11.9. Pharmacodynamic Figures

Pharmacodynamic: Figures					
No.	Population	IDSL / TST ID / Example Shell	Title	Programming Notes	Deliverable [Priority]
Part A (Single Dose): PIP Data					
4.101	Safety (Part A)	Fig 4.23 in /arenv/arprod/ gsk2269557/p ii116617/parts _cb/drivers/f_ pipratio_indiv _partcb.sas	Plot of Individual Subject Phospholipid Data in Sputum by Treatment (Single Dose)	Plot PIP3 peak area, PIP2 peak area and PIP2+PIP3 Peak Areas (geo means of reps) by treatment (x-axis). Include all subjects on one plot. Y-axis: log scale ; subject data points to be joined for each analyte. Symbols/colour to identify PIP2 peak area, PIP3 peak area etc. in legend.	SAC
4.102	Safety (Part A)	Fig 4.8 in /arenv/arprod/ gsk2269557/p ii116617/parts _cb/drivers/f_ pipratio_nottfr z_mean_partc b.sas	Plot of Adjusted Geometric Means and 90% CIs of Phospholipid Data in Sputum (Single Dose)	Y-axis: log scale PIP3 peak area Proportion and PIP3 Peak area	SAC
Part B (Repeat Dose): PIP Data					
4.201	Safety (Part B)	Fig 4.4 in /arenv/arprod/ gsk2269557/p ii116617/interi m_c/drivers/f_ pipratioindiv_ partc.sas	Plot of Individual Subject Phospholipid Data in Sputum by Treatment and Time (Repeat Dose)	PIP3 Peak Area Proportion and PIP3 Peak Area	SAC

Pharmacodynamic: Figures					
No.	Population	IDSL / TST ID / Example Shell	Title	Programming Notes	Deliverable [Priority]
4.202	Safety (Part B)	Fig 4.9 in /arenv/arprod/gsk2269557/p_ii116617/parts_cb/drivers/f_pipratio_nottfr_z_diff_partcb.sas	Plot of Adjusted Treatment Ratios and 90% CIs of Phospholipid Data in Sputum (Repeat Dose)	Y-axis: log scale PIP3 Peak Area Proportion and PIP3 Peak Area	SAC

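### In Part A the PIP3 model fits daytime both as fixed and as a plain random effect, so the 90% CIs of the adjusted geometric means rest on a variance that REML cannot estimate

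*SAP*

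**What the plan says.** SAP section 8.2.2 analyses the log of the PIP3 peak area proportion. The fixed effects are "Part A: period, treatment*daytime", and daytime takes two values in the single-dose part: "Part A: 'Day 1 3h', 'Day 1 24h". For the repeat-dose part the fixed term is "Part B: treatment*daytime*base". The section then adds, for both parts and without nesting, "Daytime and subject will be fitted as random effects".

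The data structure is given as "Repeated measures analysis based on the two replicates for each subject on each study day", and "Replicates are to be modeled using VC (variance components) structure".

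On output, the section promises "Adjusted geometric means for each treatment group will be presented along with 90% confidence intervals (CIs") and ratios to placebo at each time point. Section 10.11.9 lists Figure 4.102, "Plot of Adjusted Geometric Means and 90% CIs of Phospholipid Data in Sputum (Single Dose"), and Table 4.102 holds the matching statistical results.

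Appendix 8 (section 10.8.1) adds Kenward-Roger degrees of freedom, a structure for the R matrix and AIC to help choose that structure. It neither removes nor redefines the random daytime term.

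**The concern.** Daytime is a scheduled time point with two chosen levels, and the treatment-by-daytime term already gives every treatment its own mean at each of them. Adding daytime as a crossed random effect asks the model for a between-time variance after all between-time differences have been absorbed by fixed effects. No data are left to estimate it.

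An adjusted mean at one time carries that variance in its standard error; a difference between two treatments at the same time does not. So the displayed intervals around the Part A adjusted means would depend on what the software leaves for a component on which the data are silent. Kenward-Roger also needs the information matrix of the variance components, which is singular in this direction.

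**Working it through.** The plan states no figure on this point, so there is none to reproduce.

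**Inputs from the SAP.** Seven single-dose treatments, placebo plus six dose levels (10.4.1); two 3-period cohorts (section 1); two daytimes and two replicates (8.2.2); period and treatment-by-daytime fixed (8.2.2).

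**Assumed, because the SAP does not give them.** 8 subjects per cohort; each subject has placebo once and two active doses, with the placebo period rotating; subject SD 0.4 and residual SD 0.3 on the log scale; REML, which is usual with Kenward-Roger although the plan names no estimator; normal quantile 1.645 for 90% limits.

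**Step 1, rank.** The fixed-effect matrix X has 7 × 2 = 14 treatment-by-daytime columns plus 2 for period, rank 16. Each daytime column in Z_d is the sum of seven of the 14, so Z_d = XA for some matrix A. The rank of X with Z_d added is still 16.

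**Step 2, likelihood.** Write V = V0 + σ_d² Z_d Z_d′, where V0 holds the subject and residual parts. REML uses contrasts K′y with K′X = 0. Then K′Z_d = K′XA = 0, and σ_d² drops out. Numerically, the REML log-likelihood is identical to 6 decimals for a daytime SD of 0, 0.1, 0.2, 0.3, 0.5 and 1.0.

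**Step 3, standard errors.** Since Z_d = XA, Var(β̂) = (X′V0⁻¹X)⁻¹ + σ_d² AA′, and the estimates themselves do not change. Hence:
- mean at one daytime: SE² = SE0² + σ_d²
- difference from placebo at the same daytime: σ_d² cancels.

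For a dose group at 3 h with SE0 = 0.166 (0.161 for some doses, depending on the assumed sequences):

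| Daytime SD left by the software | SE of adjusted mean | 90% limits, ×/÷ | SE of difference from placebo |
|---|---|---|---|
| 0 | 0.166 | 1.31 | 0.140 |
| 0.1 | 0.193 | 1.37 | 0.140 |
| 0.2 | 0.260 | 1.53 | 0.140 |
| 0.3 | 0.343 | 1.76 | 0.140 |
| 0.5 | 0.527 | 2.38 | 0.140 |
| 1.0 | 1.014 | 5.30 | 0.140 |

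Example: √(0.166² + 0.3²) = √(0.0276 + 0.09) = 0.343, and exp(1.645 × 0.343) = 1.76.

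A second set of assumptions (6, 7 or 9 subjects per cohort, subject SD 0.3, residual SD 0.4) shows the same pattern for the placebo 3 h mean: ×/÷1.22, 1.20 and 1.17 at variance 0, against 1.74, 1.74 and 1.72 at variance 0.1.

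**Step 4, Part B.** With baseline as a continuous covariate in the literal three-way term, adding the daytime columns raises the rank (9 to 12 with four post-dose levels, 11 to 15 with five). The variance is estimable there, though from few levels, so the non-identifiability is confined to Part A.

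**Step 5, what happens if daytime is only deleted.** With subject as the sole random effect and independent replicate errors, two replicates of one sputum sample count as independent given subject. Suppose the sample has its own SD. Comparing the SE that the subject-only model reports on average with the true SE of the difference from placebo:
- sample SD 0.2: 0.162 against 0.190, so 1 − 0.162/0.190 = 15% too small
- sample SD 0.4: 0.215 against 0.290, so 1 − 0.215/0.290 = 26% too small.

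A cruder calculation that simply adds the sample variance to the residual gives 12% to 21%.

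**Step 6, alternative term.** A random daytime-within-subject term is identifiable: subject, subject-by-daytime and residual variances give rank 3 of 3, against 2 of 3 for subject, daytime and residual.

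**The case against.** The best defence is that the sentence is shorthand for daytime within subject. The section opens by describing replicates within subject and study day, a random term at that level makes sense, and its variance can be estimated. Under that reading the identifiability problem disappears. This may well be what was meant, but the text does not say so, and a programmer following it would code a crossed term. It does bear on the remedy: simply striking daytime is not harmless, as step 5 shows.

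The second defence is that the software may return zero, which gives exactly the interval without the term; under full maximum likelihood, zero is also where the likelihood peaked in the simulated data. This stands. The widths in the table come from imposed SDs, and no fit in the planned software was run. A reader might infer that the published intervals will be inflated; the document does not support that, only that nothing in the data fixes their width.

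A reader might also infer that the treatment comparisons are compromised. They are not in Part A: the term cancels exactly from same-time ratios, and so from the posterior probabilities of a ratio below 1. In Part B the cancellation is only approximate, but the movement found was small (in one simulated data set the log ratio went from 0.851 at a daytime SD of 0 to 0.833 at 1.0).

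**Conclusion.** The point holds for Part A as the model is written. That the daytime variance is not estimable by REML follows from algebra and does not depend on sample size or on the assumed SDs. The consequence is limited to the 90% CIs of the Part A adjusted geometric means; their point estimates, the ratios to placebo and the posterior probabilities stand. The SE of 0.166 or 0.343 for a daytime SD of 0 or 0.3 illustrates the dependence under the stated assumptions and is not a forecast. PIP3 is an exploratory endpoint, so this is a specification error worth correcting before database freeze, not a threat to the trial's main conclusions.

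**What to change.** In SAP section 8.2.2, replace "Daytime and subject will be fitted as random effects" with wording to this effect: *daytime is a fixed effect only; random effects are subject and sputum sample within subject (subject by daytime by period in Part A, subject by daytime in Part B); the sample-level component is dropped if the model does not converge.*

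This defines the intervals of the Part A adjusted means and keeps the two replicates of one sample from being treated as independent. The term belongs with the variance-components structure for replicates in 8.2.2. Combined with an unstructured R block for the replicate pair, as Appendix 8 could be read, it would be aliased with that block's covariance, so the wording should say which applies.

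The cost is one line of SAP text, one SAS statement and one extra variance component. In data this small that component may be estimated at zero, in which case the fit reduces to the subject-only model. Where sample-to-sample variation is real, the CIs of the ratios to placebo will be wider than under a subject-only model.

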10. APPENDICES

Section	Appendix
RAP Section 5 : General Considerations for Data Analyses & Data Handling Conventions	
Section 10.1	Appendix 1: Time and Events
Section 10.2	Appendix 2: Assessment Windows
Section 10.3	Appendix 3: Treatment States & Phases
Section 10.4	Appendix 4: Data Display Standards & Handling Conventions 
 • Study Treatment & Sub-group Display Descriptors • Baseline Definitions & Derivations • Reporting Process & Standards
Section 10.5	Appendix 5: Derived and Transformed Data 
 • General, Study Population & Safety • Efficacy • Pharmacokinetic • Pharmacodynamic and or Biomarkers
Section 10.6	Appendix 6: Premature Withdrawals & Handling of Missing Data 
 • Premature Withdrawals • Handling of Missing Data
Section 10.7	Appendix 7: Values of Potential Clinical Importance
Section 10.8	Appendix 8: Model Checking and Diagnostics for Statistical Analyses
Section 10.9	Appendix 9: Population Pharmacokinetic Analyses
Other RAP Appendices	
Section 10.10	Appendix 10: Abbreviations & Trade Marks
Section 10.11	Appendix 11: List of Data Displays

10.1. Appendix 1: Time & Events

10.1.1. Protocol Defined Time & Events

10.1.1.1. SOA – Part A (Single Dose)

Procedure	Part A (Single Dose) Treatment Period														Notes	
	Day -1	Day 1 (time relative to dosing)														
		Pre dose	0h	5m	30m	45m	1h	2h	3h	4h	6h	8h	12h	24h		
Admission to Unit	X															
Urine Drug/Alcohol breath test	X															
Urine Pregnancy test	X															
Brief Physical Exam	X														X	
Laboratory Assessments	X														X	
Meals	X								X						X	See Section 6.3.1 of protocol
12-lead ECG (single)		X				X					X			X	X	
Vital signs (single)		X			X		X				X		X	X		

Procedure	Part A (Single Dose) Treatment Period														Notes	
	Day -1	Day 1 (time relative to dosing)														
		Pre dose	0h	5m	30m	45m	1h	2h	3h	4h	6h	8h	12h	24h		
Telemetry		←-----→														Cardiac telemetry: To start approximately 1hr Pre-dose and then continuously for the first 5h post dose.
Spirometry (triplicate)		X					X									
Pharmacokinetic and Metabolite Profile Blood Sample		X		X	X	X	X	X	X	X	X	X	X	X		
Pharmacokinetic Urine Sample		X	←-----→													Only for the maximum proposed dose group if escalated up to (2000 µg).
Inhaler Training	X															
Dosing			X													
Sputum induction									X						X	
Adverse Event Review		←-----→														
Concomitant Medication Review		←-----→														
Discharge															X	

10.1.1.2. SOA – Part B (Repeat Dose)

Procedure	Part B (Repeat Dose) Study Day																		Notes		
	D -2 or D -1	D1	D2	D3	D4	D5	D6	D7	D8	D9	D10	D11	D12	D13	D14	D15 (D14 +24h)	D16 (D14 +48h)	D17 (D14 +72h)		D18 (D14 +96h)	
Admission to Unit	X																				
Urine Drug/Alcohol	X																				
Urine Pregnancy test	X																				
Brief Physical Exam	X																				
Laboratory Assessments	X		X ¹		X ¹		X ¹		X ¹		X ¹		X ¹		X ¹	X				1. Perform assessment pre dose	
Meals	X	X	X	X	X	X	X	X	X	X	X	X	X	X	X	X				See Section 6.3.1 of protocol	
12-lead ECG (single)	X	X ²	X ²	X ²	X ²	X ²	X ²	X ²	X ²	X ²	X ²	X ²	X ²	X ²	X ²	X				2. Perform assessments pre dose and at 30 mins post dose.	
Vital signs (single)	X	X ³	X ³	X ³	X ³	X ³	X ³	X ³	X ³	X ³	X ³	X ³	X ³	X ³	X ³	X				3. Perform assessments pre dose.	
Spirometry (triplicate)	X	X ⁴	X ⁴	X ⁴	X ⁴	X ⁴	X ⁴	X ⁴	X ⁴	X ⁴	X ⁴	X ⁴	X ⁴	X ⁴	X ⁴					4. Perform assessment pre dose and 1h post dose.	
Pharmacokinetic Blood Sample		X ⁶	X ⁵	X ⁵	X ⁵	X ⁵	X ⁵	X ⁵	X ⁵	X ⁵	X ⁵	X ⁵	X ⁵	X ⁵	X ⁶	X	X ⁷	X ⁷	X ⁷	5. pre-dose and 5 min post dose. 6. pre-dose, 5 mins, 30 mins, 45 mins, 1, 2, 3, 4, 6, 8 and 12h post dose 7. If following Single dose (SD) PK analysis deemed necessary.	

Procedure	Part B (Repeat Dose) Study Day																		Notes		
	D -2 or D -1	D1	D2	D3	D4	D5	D6	D7	D8	D9	D10	D11	D12	D13	D14	D15 (D14 +24h)	D16 (D14 +48h)	D17 (D14 +72h)		D18 (D14 +96h)	
Blood Sample for Metabolic Profiling															X ⁶	X	X ⁷	X ⁷	X ⁷		
Urea Blood Sample																X					Collect sample just before bronchoscopy
Inhaler Training	X																				
Dosing		X	X	X	X	X	X	X	X	X	X	X	X	X	X						
Sputum induction	X ¹¹	X ⁸												X ⁹ 10							8. 3h post dose 9. 3h and 24h 10. Should sputum induction fail or be insufficient at any time point then the participant will be allowed to return 24h later for a further attempt to obtain an adequate sample 11. Should sputum induction fail or be insufficient then the participant will be allowed to return 24h later for a further attempt to obtain an adequate sample. Failure to produce a baseline sample will result in participant withdrawal.

CONFIDENTIAL

202062

Procedure	Part B (Repeat Dose) Study Day																		Notes			
	D -2 or D -1	D1	D2	D3	D4	D5	D6	D7	D8	D9	D10	D11	D12	D13	D14	D15 (D14 +24h)	D16 (D14 +48h)	D17 (D14 +72h)		D18 (D14 +96h)		
Bronchoscopy																X						
Adverse Event Review		←-----→																				
Concomitant Medication Review		←-----→																				
Discharge																	X					

10.2. Appendix 2: Assessment Windows

10.2.1. Definitions of Assessment Windows for Analyses

Analysis Set / Domain	Parameter (if applicable)	Target	Analysis Window		Analysis Timepoint
			Beginning Timepoint	Ending Timepoint	
e.g. "Safety", "Efficacy" or list specific domains if required	e.g. "All" or list specific parameters (i.e. tests) if required	The target or most desired relative day or relative time value for a given visit. e.g. "Day 7"	e.g. "Day 1"	e.g. "Day 10"	e.g. VISIT 1
Pharmacodynamic	Sputum PIP data	Day -2 or Day -1 (Part B)	Predose		PREDOSE
		Day 1 3h (Parts A and B)	Day 1 2h45m	Day 1 3h15m	Day 1 3h
		Day 1 24h (Part A)	Day 1 22h30m	Day 1 25h30m	Day 1 24h
		Day12 3h (Part B)	Day 12 ¹ 2h45m	Day 12 ¹ 3h15m	Day 12 3h
		Day 12 24h (Part B)	Day 12 ¹ 22h30m	Day 12 ¹ 25h30m	Day 12 24h

NOTES :

- All other data will be summarised using the planned timepoint.

[1] Note that if subject is unable to provide a sputum sample on Day 12, then they may have another attempt on Day 13. If this happens then the Day 12 windowing timing will be relative to the Day 13 dose rather than the Day 12 dose.

10.3. Appendix 3: Treatment States and Phases

10.3.1. Treatment Phases

Assessments and events will be classified according to the time of occurrence relative to study treatment unless otherwise specified.

Treatment Phase	Definition
Pre-Treatment	Date \leq Study Treatment Start Date
On-Treatment	Study Treatment Start Date < Date \leq Study Treatment Stop Date
Post-Treatment	Date > Study Treatment Stop Date

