10.3.2.1. Treatment States for Concomitant Medication Data

Treatment State	Definition
Pre-Treatment	Medication End Date \leq Study Treatment Start Date
On-Treatment	Study Treatment Start Date \leq Conmed Start Date \leq Study Treatment Stop Date Study Treatment Start Date \leq Conmed End Date
Post-Treatment	ConMed Start Date > Study Treatment Stop Date

NOTES:

- If the study treatment stop date is missing then the assessment will be considered to be On-Treatment

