10.3.2.2. Treatment States for AE Data

Treatment State	Definition
Pre-Treatment	AE Start Date < Study Treatment Start Date
On-Treatment	If AE onset date is on or after treatment start date & on or before treatment stop date. Study Treatment Start Date \leq AE Start Date \leq Study Treatment Stop Date
Post-Treatment	If AE onset date is after the treatment stop date. AE Start Date > Study Treatment Stop Date
Onset Time Since 1 st Dose (Days)	If Treatment Start Date > AE Onset Date = AE Onset Date - Treatment Start Date If Treatment Start Date \leq AE Onset Date = AE Onset Date - Treatment Start Date + 1 Missing otherwise.
Duration (Days)	AE Resolution Date – AE Onset Date + 1
Drug-related	If relationship is marked 'YES' on PIMS OR value is missing.

NOTES:

- If the study treatment stop date is missing then the AE will be considered to be On-Treatment.

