10.5.2. Study Population

Demographics

Age

- Age will be calculated based on year of birth compared to the date of the screening visit.
- GSK standard IDSL algorithms will be used for calculating age where birth date will be imputed as follows:
 - Any subject with a missing day will have this imputed as day ‘15’.
 - Any subject with a missing date and month will have this imputed as ‘30th June’.
- Birth date will be presented in listings as ‘YYYY’.

Body Mass Index (BMI)

- Calculated as **Weight (kg) / (Height (m))²**

Extent of Exposure

- Number of days of exposure to study drug will be calculated based on the formula:
Duration of Exposure in Days = Treatment Stop Date – (Treatment Start Date) + 1
- Subjects who were randomized but did not report a treatment start date will be categorised as having zero days of exposure.
- The cumulative dose will be based on the formula:
Cumulative Dose = Sum of (Number of Days x Total Daily Dose)
- If there are any treatment breaks during the study, exposure data will be adjusted accordingly.

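### SAP 10.3.1 puts the treatment start date in Pre-Treatment, so by calendar date post-dose values on the dosing day are labelled Pre-Treatment; the displays exposed are few, chiefly the 'Emergent' QTc tables

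*SAP*

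**What the plan says.** SAP 10.3.1 sorts assessments and events into three phases and yields where another rule is given. Pre-Treatment is "Date \leq Study Treatment Start Date", On-Treatment is "Study Treatment Start Date < Date \leq Study Treatment Stop Date", and Post-Treatment is any date after the stop date. The introductory sentence speaks of time, but the definitions use dates. The section does not say whether start and stop in Part A belong to each period or to the whole sequence.

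Four other places bear on this:

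- **10.5.2, Extent of Exposure**, uses the same two variables as calendar dates: "Duration of Exposure in Days = Treatment Stop Date – (Treatment Start Date) + 1".
- **10.3.2.2, AE states**, sets On-Treatment as "If AE onset date is on or after treatment start date & on or before treatment stop date", so the start date is included.
- **10.3.2.1, con-med states**, sets Pre-Treatment as "Medication End Date \leq Study Treatment Start Date", while one of its two On-Treatment lines is "Study Treatment Start Date \leq Conmed End Date".
- **10.2.1** gives sputum windows and then states: "All other data will be summarised using the planned timepoint".

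Six tables in 10.11.4 carry 'Emergent' in the title (2.106, 2.108, 2.110, 2.206, 2.208, 2.210). The SAP does not define the word.

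**The concern.** A drug effect can be seen only after the dose, and in Part A most post-dose safety assessments fall on the dosing day itself. A rule that assigns that whole day to Pre-Treatment labels those values as if the drug had not been given. An AE and an ECG abnormality on the same dosing day would then carry different labels.

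What is at stake is any display or dataset flag that selects by phase or state. Safety is the primary endpoint. The maximum-QTc tables are the most exposed: if a programmer takes 'Emergent' to mean On-Treatment, ECGs taken soon after dosing could drop out of the table meant to show the highest post-dose QTc.

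**Working it through.** No sample size or error rate is involved, so the check is to apply the inequalities as written.

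**Inputs**

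- Part A has one dosing mark per period, at 0 h (10.1.1.1). With per-period dates, Start = Stop. The 10.5.2 formula then gives Stop − Start + 1 = 1 day.
- Part B doses on Days 1 to 14, with a 30-minute post-dose ECG each day (10.1.1.2): 14 such ECGs.
- Part A post-dose ECGs on the dosing day: the schedule table is damaged in extraction. By column position, marks fall at 45 min and 6 h. Both stay on the dosing day if the columns are off by one either way, so 2 per period is a floor: 2 × 3 periods = 6. Later marks are left out.
- Assumptions: morning dosing, more than one day between periods and, for date-time, a stop time equal to the start time.

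**Part A, one period, Start = Stop**

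- *By date:* the dosing day meets Date ≤ Start, so it is Pre. The next day exceeds Stop, so it is Post. No date satisfies Start < Date ≤ Stop.
- *By date-time:* 0 h is Pre and everything from 5 min to 24 h is Post. If the stop time were 5 min after the start, only values up to 5 min would be On; 30 min onward would still be Post.
- *AE rule, by date:* day before = Pre, dosing day = On, next day = Post.

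**ECG counts under each reading**

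| Reading | Part A per-period dates: On / Pre / Post of 6 | Part A first-to-last dose: On / Pre / Post of 6 | Part B 30-min ECGs On, of 14 |
|---|---|---|---|
| Calendar date | 0 / 6 / 0 | 4 / 2 / 0 | 13 (Day 1 is Pre) |
| Date-time | 0 / 0 / 6 | 4 / 0 / 2 | 13 (Day 14 is Post) |
| Start as date-time, stop as whole day | 6 / 0 / 0 | 6 / 0 / 0 | 14 |

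With first-to-last dates, Period 1 is lost by date and Period 3 by date-time; each costs 2 of 6. The last row classifies every dosing-day ECG sensibly, but the SAP does not state that reading.

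**Part A laboratory sets.** The only post-dose mark shares a column with the second sputum mark, which 10.2.1 places at 24 h. With per-period dates these sets are Post in 3 of 3 periods under all three readings, and they would be Post under the AE boundaries too. That comes from the stop boundary, not the start-date rule.

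**Con-meds.** Take a medication that starts and ends on the start date. End ≤ Start holds, so it is Pre. Start ≤ con-med start ≤ Stop and Start ≤ con-med end both hold, so it is also On, however the two On lines are joined. The SAP does not say how they are joined. If either suffices, a medication begun after Stop is both On and Post. If both are required, one begun before dosing and continuing past the start date has no state.

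**The case against.** The strongest reply is that no display is shown to use the phase rule. Appendix 11 never says a table selects by phase. By-visit summaries use the planned timepoint (10.2.1), baseline is the latest pre-dose assessment, per period in Part A (10.4.2.1), and AEs have their own rule. For the PCI tables, 10.5.1 points to a post-baseline basis. Nothing says Tables 1.109 and 1.209 select con-meds by state. All of this stands, and it confines the consequence mainly to Tables 2.110 and 2.210.

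Three stronger readings are tempting and are not supported:

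- **That Part A has no on-treatment time at all.** This needs per-period dates, which the SAP does not state. With first-to-last dates, 4 of the 6 ECGs are On-Treatment.
- **That the AE rule contradicts 10.3.1.** The general rule gives way where another is specified, and 10.3.2.2 specifies another. The two domains label the same date differently, but there is no conflict over AEs.
- **That vital signs and spirometry belong in the count.** Neither has an 'Emergent' table; both go to other summaries (2.112, 2.113, 2.212, 2.213), so they cannot be lost from the tables at issue.

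What the reply does not remove is that the written inequalities misplace the dosing day by date and, by date-time, give a single-dose period no usable On-Treatment window.

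**Conclusion.** The point holds as a minor wording fault with a narrow reach. By calendar date, 10.3.1 classes post-dose values on the first dosing day as Pre-Treatment; with per-period dates this is true of every Part A dosing day. By date-time the start boundary is right, but all post-dose values in a single-dose period fall into Post-Treatment. The con-med states overlap on any reading.

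Exposure, in order of likelihood: QTc Tables 2.110 and 2.210; then the PCI tables 2.106, 2.108, 2.206 and 2.208, less likely given 10.5.1; and con-med Tables 1.109 and 1.209 if they select by state. At least 2 dosing-day post-dose ECGs per Part A period (6 per subject over three periods) and 1 of 14 Part B 30-minute ECGs could be misclassified. These counts assume that 'Emergent' is taken as On-Treatment, per-period dates in Part A, a date-only or date-time-only reading, and the schedule assumptions above.

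A reader might infer that the safety results as a whole would be wrong. The document does not support that: by-visit summaries, baselines and all-AE tables do not depend on phase.

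**What to change.** 1. **10.3.1.** State that start and stop are per period in Part A, and the first and last dose in Part B. Set Pre-Treatment as before that (first) dose, by date-time or by planned pre-dose timepoint, and On-Treatment as after it. Where only a date is held, count the dosing date as On-Treatment, as 10.3.2.2 does. Read the stop date as a whole calendar day; changing < to ≤ alone repairs only the calendar-date reading.
2. **'Emergent' tables (2.106, 2.108, 2.110, 2.206, 2.208, 2.210).** Define 'Emergent' as any value after the dose in that period (Part A) or after the first dose (Part B). The 24 h and Day 15 values then count whatever their phase.
3. **10.3.2.1.** Pre = ended before the start date. On = started on or before the stop date, and ended on or after the start date or ongoing. Post = started after the stop date. Each medication then has exactly one state.

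Leave the AE end boundary in 10.3.2.2 unchanged. No fault in it is shown, and extending it by a day would make events on Day 15, the bronchoscopy day in Part B, On-Treatment.

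The cost is SAP wording and a small derivation change. Actual times relative to dosing are already held for listings (10.4.3), and AEs and con-meds have full dates (10.6.2.1), so no new data are needed.
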